3.3 Adaptive Design

Not applicable

4. Covariates and Subgroups**4.1 Planned Covariates**

Baseline values may be used as a covariate in analyses.

4.2 Subgroups

No subgroup analyses are planned.

5. Definitions**Actual Treatment Group:**

A subject's actual treatment group is the randomized treatment group unless more doses of the other treatment (placebo or AMG 133) are received than the randomized treatment.

Age:

Subject age at randomization will be determined using the age in years reported in the clinical database.

Treatment-emergent Adverse Event:

A TEAE is any AE that is categorized as an AE starting on or after first dose of investigational product (IP) as determined by the flag indicating if the AE started prior to the first dose on the Events case report form and up to the end of study date.

Baseline:

For any variable, unless otherwise defined, baseline is the last non-missing assessment taken prior to the first dose of IP.

Baseline ECG Parameters:

Baseline ECG will be calculated as the average of the available pre-dose observations taken on Day 1. If any of the observations are missing, the mean will be calculated by taking the available observations. If all Day 1 pre-dose observations are missing, the baseline will be calculated in the same way using the last assessment before first dose of IP.

Change from Baseline:

The arithmetic difference between a post-baseline value and the baseline value from a given variable at a given time point is defined as:

Change from baseline = (post-baseline value at given time point – baseline value).

Percent Change from Baseline:

The percent change from baseline for a given variable at a given time point is defined as:

Percent change from baseline = $([\text{post-baseline value at given time point} - \text{baseline value}] / \text{baseline value}) \times 100$.

Investigational Product:

The IPs are defined as AMG 133 or placebo.

Subject-level End of Study Date:

End of study for each subject is defined as the date the subject last completed a protocol-specified procedure. The date will be recorded on the End of Study CRF page.

Study End Date:

The study end date is the last end of study (EOS) date of all randomized subjects.

Primary Completion:

The primary completion date is defined as the date when the last subject is assessed or receives an intervention for the final collection of data for the primary endpoints.

If the study concludes prior to the primary completion date originally planned in the protocol (i.e., early termination of the study), then the primary completion will be the date when the last subject is assessed or receives an intervention for evaluation in the study (i.e., last subject last visit).

Study Day 1:

Day 1 is defined as the date that the first dose of IP is administered.

Study Day:

For each subject and a given date of interest, study day is defined as the number of days since Study Day 1:

Study Day = (date of interest – Study Day 1 date) + 1.

If the date of interest is prior to the Study Day 1:

Study Day = (date of interest – Study Day 1 date).

IP Exposure Period in Weeks

For subjects dosed with IP:

$(\text{Last Dose Date of IP} - \text{date of Study Day 1} + 1) / 7$

Study Exposure Period in Weeks

For each randomized subject:

$(\text{EOS Date} - \text{Randomization Date} + 1) / 7$

Fridericia-corrected QT Interval:

The Fridericia-corrected QT interval (QTcF) will be calculated from the investigator reported QT (msec) and RR interval (msec), as follows: $\text{QTcF} = \text{QT} / (\text{RR}/1000)^{1/3}$.

Data Cutoff Date for Interim Analysis:

The first interim analysis data cutoff date will be approximately 36 days after cohort 9 enrollment. The second interim analysis data cutoff date will be after all subjects in cohorts 1 to 11 have completed the study.

6. Analysis Sets**6.1 Full Analysis Set**

The full analysis set (FAS) will consist of all randomized subjects who receive at least one dose of IP.

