Part C: Cohorts 12 - 13: Subjects who meet all the screening inclusion criteria and none of the exclusion criteria will be eligible to report to the research facility once on day -2 (up to day -4), at which time assessments will be performed to confirm eligibility. If subjects are eligible after the completion of all day -2 assessments, subjects will receive AMG 133 on day 1.

Day -1

Part A: Cohorts 1 to 5 and cohort 11: A [REDACTED] test will be performed on day -1 along with additional procedures as outlined in the Schedule of Activities in **Section 1.3.** As part of the [REDACTED]

summarized in the Schedule of Activities in **Section 1.3**. [REDACTED] tests will not be performed in cohort 6.

Part B: cohorts 7 to 10: Subjects who meet all the screening inclusion criteria and none of the exclusion criteria will be eligible to report to the research facility on day -1, at which time assessments will be performed to confirm eligibility. If subjects are eligible after the completion of all day 1 assessments, subjects will be randomized to receive either AMG 133 or placebo on day 1.

Day 1:

Part A: After completion of all predose procedures on the day of dosing (day 1), subjects will receive investigational product (SC for cohorts 1 to 5 and cohort 11 and IV for cohort 6, only). Subjects will undergo vital signs and pharmacokinetics blood draws postdose as outlined in the Schedule of Activities in **Section 1.3**.

Part B: After completion of all predose procedures on the day of dosing (day 1), subjects will receive investigational product (SC for cohorts 7 to 10). Subjects should undergo additional vital sign assessments 3 hours after dosing but are not scheduled to get postdose blood draws on day 1 (see Schedule of Activities in **Section 1.3**).

Part C: After completion of all predose procedures on the day of dosing (day 1), subjects will receive AMG 133 (SC). Subjects are scheduled to get postdose blood draws on day 1 but should undergo additional monitoring (per clinical site standard operating procedures) and vital sign assessments approximately 4 to 5 hours after dosing. The subjects can be discharged from the clinical facility based upon a stable vital signs and assessment per clinical site standard operating procedures.

Day 7

Cohorts 1 to 5 and cohort 11: A [REDACTED] test will be repeated on day 7 along with additional procedures as outlined in the Schedule of Activities in **Section 1.3**.

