6.4 Measures to Minimize Bias: Randomization and Blinding

6.4.1 Method of Treatment Assignment

Subjects will be randomized in a 3:1 allocation ratio, to AMG 133 to placebo, respectively, in double-blind manner **in Part A and Part B cohorts 1 to 11 only. Part C cohorts 12 to 13 is an open-label study.**

The randomization will be performed by IRT.

Subjects will be assigned a randomization number based in sequential order in which they qualified to be randomized. Subjects will be considered randomized once a unique subject randomization number has been assigned.

The randomization date is to be documented in the subject's medical record and on the enrollment CRF.

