9.3 Analysis Sets, Subgroups, and Covariates

9.3.1 Analysis Sets

9.3.1.1 Full analysis Set

The full analysis set will consist of all randomized subjects who receive at least 1 dose of AMG 133.

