INR	international normalized ratio
IPIM	Investigational Product Instruction Manual
IRB	Institutional Review Board
IRT	interactive response technology that is linked to a central computer in real time as an interface to collect and process information
IV	intravenous
Kd	dissociation constant
mAb	monoclonal antibody
MAD	multiple ascending dose
MRSD	maximum recommended starting dose
NCT	National Clinical Trials
NOAEL	no observed adverse effect level
PHQ-9	Patient Health Questionnaire-9
PD	pharmacodynamics
PK	pharmacokinetics
QTc	corrected QT interval
QW	every week
Q4W	every 4 weeks

Randomization	defined as once a unique subject randomization number has been assigned through IRT at enrollment
SAD	single ascending dose
SC	subcutaneous
Source Data	Information from an original record or certified copy of the original record containing patient information for use in clinical research. The information may include, but is not limited to, clinical findings, observations, or other activities in a clinical study necessary for the reconstruction and evaluation of the study. Source data are contained in source documents (original records or certified copies). (ICH Guideline [E6]). Examples of source data include Subject identification, Randomization identification, and Stratification Value.
TBL	total bilirubin
t_{max}	time of maximum observed concentration
ULN	upper limit of normal

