6.2 Safety Analysis Set

The safety analysis set is the same as the FAS

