9.6 Safety Analyses

9.6.1 Analyses of Primary Safety Endpoint(s)

A table summarizing the primary endpoints and planned analysis methods is shown below:

Table 9-1. Primary Endpoint Summary Table

| Endpoint | Statistical Analysis Method | Sensitivity Analysis |
|--|---|-----------------------------|
| Subject incidence of TEAEs | 
The following analyses will be performed on the FAS and summarized by dose phase (SAD cohorts in Part A and MAD cohorts in Parts B to C) and actual treatment group.
 
Subject incidence tabulated by system organ class (SOC), high level term (HLT), and preferred term (PT) of
 
 • TEAEs • fatal AEs • serious adverse events (SAEs) • AEs leading to withdrawal from IP or other protocol-required therapies | None |
| Changes in laboratory safety tests, vital signs and 12-lead ECGs | 
The following analyses will be performed on the FAS and summarized by dose phase (SAD cohorts in Part A and MAD cohorts in Parts B to C) and actual treatment group at protocol-specified scheduled visit.
 
Summary statistics of
 
 • change from baseline safety laboratory test results | None |

| | | |
|--|--|--|
| | 
• change from baseline vital signs• change from baseline ECG parameters | |
|--|--|--|

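### The SAP limits the FAS and safety set to randomized subjects, which read literally leaves non-randomized, open-label Part C out of the primary safety tables meant to include it

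*SAP*

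**What the plan says.** SAP 6.1 defines the full analysis set: "The full analysis set (FAS) will consist of all randomized subjects who receive at least one dose of IP". SAP 6.2 adds: "The safety analysis set is the same as the FAS". Protocol 9.3.1.1 has the same randomization condition: "The full analysis set will consist of all randomized subjects who receive at least 1 dose of AMG 133". (It names AMG 133 where the SAP names IP. That is a separate difference and nothing here rests on it.)

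Protocol 6.4.1 applies randomization "in Part A and Part B cohorts 1 to 11 only. Part C cohorts 12 to 13 is an open-label study". The Day -2 text for Part C in the protocol synopsis contains no randomization step: "If subjects are eligible after the completion of all day -2 assessments, subjects will receive AMG 133 on day 1". The matching text for Parts A and B says that eligible subjects will be randomized.

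SAP Table 9-1 (section 9.6.1) says that the adverse event, laboratory, vital sign and ECG analyses are "performed on the FAS and summarized by dose phase (SAD cohorts in Part A and MAD cohorts in Parts B to C", and then by actual treatment group. SAP 5 defines that group as the randomized group, unless the subject received more doses of the other treatment.

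**The concern.** Safety and tolerability are the primary objective. Protocol 4.3 gives the purpose of Part C as studying first-dose gastrointestinal adverse events under titration, so its safety tables are its main product. Applied to the letter, the set definition leaves those tables with no subjects, while Table 9-1 calls for them.

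The second gap is different in kind. The treatment group definition does not remove Part C subjects; it gives them no value. Even if they are admitted to the FAS, the SAP does not say which column they belong in, or whether cohorts 12 and 13 are shown apart. A programmer would have to settle both points without a written rule.

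**Working it through.** **Inputs.** AMG 133 subjects (SAP 3.2, same in protocol 9.2): 42 in Part A, 18 in cohorts 7 to 9, up to 15 in cohort 10, up to 12 in Part C. All subjects (protocol 4.2): 56 in Part A, 24 in cohorts 7 to 9, up to 20 in cohort 10, up to 12 in Part C. All figures below use these planned maxima.

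**Step 1: reproduce the plan's figures.** 42 + 18 + 15 + 12 = 87. The chance of seeing at least one event with true incidence p among n subjects is 1 − (1 − p)^n.
- p = 3%: 1 − 0.97^87 = 0.92935, or 92.9%, as stated.
- p = 5%: 1 − 0.95^87 = 0.98847, or 98.8%, as stated.

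**Step 2: apply the safety set as written.** Removing Part C leaves 87 − 12 = 75 AMG 133 subjects.
- p = 3%: 1 − 0.97^75 = 0.89817, or 89.8%.
- p = 5%: 1 − 0.95^75 = 0.97866, or 97.9%.

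The whole planned FAS would be 56 + 24 + 20 = 100 subjects instead of 112.

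**Step 3: share of the data affected.**
- All AMG 133 subjects: 12/87 = 13.8%.
- AMG 133 subjects in the multiple-dose phase: 18 + 15 + 12 = 45, and 12/45 = 26.7%.

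**Step 4: is inclusion intended?** Table 9-1 is the one place that directly pairs the FAS with Part C. Four others show intent without mentioning the FAS:
- SAP 3.2 counts 12 Part C subjects in its 87.
- SAP 7.3 bases the final analysis on cohorts 1 to 13.
- SAP Table 9-2 names cohorts 12 to 13 for high-sensitivity CRP.
- Protocol 9.4.2.1 requires cohorts 12 to 13 to be summarized separately.

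The pharmacokinetic set in SAP 6.3 has no randomization condition and already admits Part C.

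**Step 5: could a Part C subject count as randomized?** Protocol 6.4.1 says: "Subjects will be considered randomized once a unique subject randomization number has been assigned". The protocol glossary (Appendix 1) defines randomization alike, "defined as once a unique subject randomization number has been assigned through IRT at enrollment", and its entry for enrollment has the investigator assign a randomization number. Protocol 4.2 speaks of Part C subjects as enrolled. Chained together, these suggest that an enrolled Part C subject holds a number and so is randomized. Against that, protocol 6.4.1 expressly limits randomization to cohorts 1 to 11, and protocol 5.4 defines enrollment by eligibility alone. The express limit is the better reading. Even on the other reading, Part C would have no randomized arm, and the treatment group would still be undefined.

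**The case against.** The strongest reply is that nobody will be misled. The intent to include Part C is plain, no hypothesis is tested, and the dose level review of Part C safety data does not depend on the FAS. That stands, and it limits the severity: empty tables are unlikely in practice. It does not make the definition right. An analysis population should not depend on staff disregarding its wording, and intent on inclusion does not settle how Part C is presented.

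The glossary on enrollment is real counter-evidence. It does not prevail, for the reasons in step 5, but it does affect how the fix should be worded.

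A reader might also infer more than the documents support:
- *That the treatment group rule excludes Part C as well.* It excludes nobody; it leaves Part C without a group.
- *That the SAP 9.2 disposition table would be wrong.* For the multiple-dose phase it could show at most 24 + 20 = 44 randomized and up to 44 + 12 = 56 who received IP. Both counts would be true, because Part C is not randomized. The wording is incomplete for Part C, but the difference of 12 measures no error.
- *That the sponsor chose to leave Part C out, or that the detection figures are miscalculated.* The sections in step 4 point the other way on the first, and step 1 reproduces the figures.

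**Conclusion.** The concern holds as a drafting error in current text that should be fixed. As written, the FAS and safety set exclude up to 12 of 87 AMG 133 subjects (13.8%; 26.7% in the multiple-dose phase) from primary safety tables that Table 9-1 says cover Parts B to C. The 92.9% and 98.8% figures are correct for 87 dosed subjects, but describe the safety set only once Part C is in it. The treatment group gap is a second, separate omission.

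This rests on full planned enrolment and on taking protocol 6.4.1's limit to cohorts 1 to 11 at its word. The effect is confined to Part C: no cohort 1 to 11 summary changes, and both interim analyses, which stop at cohort 11, are untouched.

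**What to change.** In the SAP:
- **6.1 and 6.2:** define the FAS and safety set as all subjects who receive at least one dose of IP, randomized in Parts A and B and open-label in Part C. Base the condition on dosing and not on enrollment, because the protocol glossary ties enrollment to a randomization number.
- **5, Actual Treatment Group:** for Part C, use the cohort regimen received. Summarize cohorts 12 and 13 separately, as in protocol 9.4.2.1.
- **5, Study End Date and Study Exposure Period:** both now refer only to randomized subjects. Base the first on all dosed or randomized subjects, and start the second from Study Day 1 for Part C.
- **10:** record the change to the FAS.
- **Housekeeping:** extend the disposition and by-site wording in 9.2 to Part C, and delete cohorts 12 to 13 from the placebo pooling in 9.1. Part C has no placebo arm, so the deletion removes no records.

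Align protocol 9.3.1.1 at the next amendment made for other reasons. This point alone does not justify one, since amendments must go to the IRB/IEC. The cost is a few sentences, with no new data.

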6.2 Safety Analysis Set

The safety analysis set is the same as the FAS

6.3 Pharmacokinetic Analyses Set(s)

The pharmacokinetics analysis set (PKAS) will consist of all subjects who receive at least one dose of AMG 133 for whom at least one concentration post-dose or PK parameter or endpoint can be adequately estimated.

6.4 Interim Analyses Set(s)

The interim analysis set will be an interim version of the FAS which will consist of all observations that have occurred up to the cutoff date for the interim analysis. Refer to [Section 7.1](#) for details of the interim analysis.

7. Planned Analyses**7.1 Interim Analysis and Early Stopping Guidelines**

[figure not shown]
The DLRM members will oversee progress of the study and make recommendations relating to early closure/extension or alteration of the study based on ongoing monitoring of the study data. Refer to [Section 11.3](#) of the protocol for further details.

The first administrative interim analysis will be conducted after the DLRM for cohort 9 with no preplanned adaptive decisions. The objective of the interim analysis is to obtain preliminary information for planning subsequent trials. This analysis will include data from cohorts 1 to 9. If cohort 10 and 11 has undergone DLRM prior to the DLRM for cohort 9, data from these cohorts may be included in the analysis as well. For the first interim analysis, the data cutoff is 36 days after the last subject in cohort 9 is enrolled. At that time, the database will be cleaned, processed, and a snapshot for cohorts 1 to 9 and, if applicable, an “as is” snapshot for cohorts 10 and 11 will be taken.

The analysis performed at the first interim analysis will include:

- Assessment of the primary endpoints:
 - subject incidence of TEAEs

- changes in laboratory safety test (see [Table 9-2](#))
- changes in vital signs
- changes in 12-lead ECGs
- Assessment of the secondary endpoints:
 - PK parameters
 - incidence of antidrug antibodies (ADA)
- Assessment of the exploratory endpoints:

The second interim analysis will occur after all subjects in cohorts 1 to 11 have completed the study. For the second interim analysis, the data cutoff is at EOS. At that time, the database will be cleaned, processed, and a snapshot for cohorts 1 to 11 will be taken. The second interim analysis will include all time points and all planned analysis similar to the final analysis with the exception that the data generated from the [REDACTED] [REDACTED] will not be included in the second interim analysis. The study will be unblinded to sponsor staff conducting and reviewing the interim analysis and remain blinded to site personnel and site-facing staff of the sponsor.

7.2 Primary Analysis

The primary analysis will occur at the final analysis and not be a separate analysis.

7.3 Final Analysis

The final analysis will occur after all subjects in cohort 1 to 13 have completed this study. Data will be locked prior to conducting the final analysis based on a clean snapshot of data from cohorts 1 to 13.

8. Data Screening and Acceptance**8.1 General Principles**

The objective of the data screening is to assess the quantity, quality, and statistical characteristics of the data relative to the requirements of the planned analyses.

8.2 Data Handling and Electronic Transfer of Data

For the interim and final analyses, the Amgen Global Study Operations-Data Management department will provide all data to be used in the planned analyses, except as indicated below for the Analysis Dataset for PK Concentrations (ADPC). This study will use the RAVE database.

The ADPC will be provided to Clinical Pharmacology Modeling and Simulation (CPMS) from Global Statistical Programming.

8.3 Handling of Missing and Incomplete Data

Laboratory measurements that are below the quantification limits will be considered equal to the lower limit of quantification (LLQ) for the calculation of population averages in summary tables. There will be no imputation of clinical laboratory values below LLQ for individual subject level data in the line listings, as applicable.

PK concentration that are below the quantification limits will be set to zero when engaging non-compartmental model to compute PK parameters.

AE and concomitant medication with completely or partially missing dates will be queried. If the date is still incomplete with year only or year and month only after the query (i.e., partially missing date information), the start date will be imputed as described in [Appendix A](#).

8.4 Detection of Bias

Protocol compliance will be examined by listing important protocol deviations (IPD) by cohort and site.

8.5 Outliers

Outliers may be identified by the use of descriptive statistics. All data confirmed as an outlier will not be excluded in the interim or final analyses described in this SAP.

If outliers exist a sensitivity analysis eliminating or reducing the outlier effect may be performed and differences between their results may be reviewed if required.

PK plasma concentration data will be evaluated for outliers by visual inspection, and decision to re-assay individual samples will be made in accordance with standard PK evaluation practice.

8.6 Distributional Characteristics

Where appropriate, the assumptions underlying the proposed statistical methodologies will be assessed.

8.7 Validation of Statistical Analyses

Programs will be developed and maintained and output will be verified in accordance with current risk-based quality control procedures.

Tables, figures, and listings will be produced with validated standard macro programs where standard macros can produce the specified outputs.

The production environment for statistical analyses consists of Amgen-supported versions of statistical analysis software; for example, the Statistical Analysis Software System version 9.4 or later.

9. Statistical Methods of Analysis**9.1 General Considerations**

Descriptive statistics will be provided for selected demographics, safety, PK, and PD endpoints. Accumulating PD data might be reviewed throughout the study by treatment, periodically.

Descriptive statistics on continuous measurements will include means, medians, 25th and 75th percentiles, standard deviations and ranges, while categorical data will be summarized using frequency counts and percentages. PK, PD, and clinical laboratory data will be summarized by dose phase (SAD cohorts in Part A and MAD cohorts in Parts B to C) and actual treatment group at each protocol-specified scheduled visit.

Data for subjects receiving placebo will be combined across SC injection for cohorts 1 to 5, cohort 11, and IV for cohort 6, except for AEs where the combined SC cohorts will be summarized separately from the IV cohort within Part A.

Data for subjects receiving placebo will be combined across cohorts 7 to 9 and cohorts 12 to 13 within Parts B to C and data for subjects receiving placebo from cohort 10 will be summarized separately.

Data for subjects receiving AMG 133 will be presented separately by dose phase (SAD cohorts in Part A and MAD cohorts in Parts B to C) and actual treatment group. When data are summarized by time, the values recorded against the scheduled time points listed in the protocol will be used. When assessing minimum/maximum increases or decreases over the study, all assessments, including unscheduled assessments will be used.

